Inclusion: ≥ 18 years old, $\text{BMI} \geq 28 \text{ kg/m}^2$ AND one additional CVRF, access and willingness to engage in digital technology, has a valid email address and a cell phone number, and able to ambulate and speak/read English

Exclusion: Class III/IV heart failure, MI or cardiac surgery in prior 3 months, severe renal/hepatic disease, active malignancy, current/recent (within 6 months) enrollment in weight loss program.

b. Participants will be recruited when they are being followed for the management of their atrial fibrillation in the Stanford clinic.

c. Procedure: Individuals meeting inclusion criteria, but not excluded, will be invited to participate. Once consented, demographics, biometrics and baseline measures will be collected. Both groups will be asked to enter initial responses into AF CARE and then will be randomized to either the digital platform AF CARE group and UC or Wait List Group. The UC wait list group will receive usual care for the first 3 months and then they will receive the digital platform (AF CARE) after 3 months of enrollment. Both groups will be appropriately referred for smoking cessation, behavioral medicine, endocrinology, and/or sleep clinic during initial and Month 3 visit, based on screening completed at that visit. Initial measures will be collected, and repeated at Month 3, Month 6, and Month 12.

Both AF CARE/UC and Wait List Groups	Initial	Month 3 (CA)	Month 6	Month 12
Medical History and Physical	X	X	X	X
Demographics	X			
Psychographic score	X			
AHA Life's Simple 7	X	X	X	X
Biometrics- pt reported (BP, HR, RR, waist, BMI)	X	X	X	X
Blood testing, if available: Lipid panel, Blood Sugar	X		X	X
6 Minute Walk Test	X	X	X	X
Jessa AF Knowledge Questionnaire	X	X	X	X
AF Symptom Severity Scale (AFSS)	X	X	X	X

Ambulatory Monitor (Zio patch)- if available	X	X	X	X
AF Effect on Quality of Life (AFEQT)	X	X	X	X
AF CARE Group -Access to AF CARE	X-----→			
Wait List Access to AF CARE	X-----→			

AF CARE GROUP: Patients will receive personalized messages twice weekly that will include behavior recommendations for CVRF reduction and AF education from the AHA library. Messages will be patient-specific based on the initially entered psychographic profile and data entered.

Ongoing messages will include participant response requests and future messages elicited by AF CARE will be based on entered responses.

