During the protocol, 3 participant non-responses to communications will result in a message being sent to the research team to prompt a call to the participant to enforce the importance of the messaging. In addition, a participant posting a negative response (e.g. "I do not know how to get my medicine refilled") will also result in a message being sent to the research team to determine if clinical follow-up is required.

Wait List UC Group/AF CARE Group: Participants will be given a weight loss goal of 10% and other recommendations for CVRF reduction based on their initial LS7 assessment. They will be provided written educational materials to review independently on AF and AF CA treatment.

Participants in this group will receive personalized messages twice weekly that will include behavior recommendations for CVRF reduction and AF education from the AHA library starting at 3 months following randomization. Measurable Outcomes: (See Table above).

- a. CVRF will be evaluated using the pre-post measures of the AHA Life's Simple 7, along with patient reported blood pressure, BMI, blood tests (lipids and glucose), and 6-minute walk test.
- b. AF knowledge will be evaluated with the Jessa AF Knowledge Questionnaire
- c. AF Symptom Severity and Burden will be measured with the AF Symptom Severity Scale
- d. QOL will be measured with the AF Effect on Quality of Life Questionnaire, and the Patient Health Questionnaire-9

Data Analysis: Demographic data will be analyzed using descriptive statistics for continuous data and frequencies and percentages for categorical data.

The feasibility of AF CARE will be determined by calculating acceptability, demand, AF CARE usage, adherence, and qualitative interview data analysis.

Efficacy will be evaluated on CVRF, AF Knowledge, AF symptom severity and burden, and QOL using matched pair t-tests at baseline, 3 and 6, and 15 months to determine the differences between and within groups. This data will be used to calculate the sample size required in a future multicenter trial designed to achieve 80% power to detect a change of 10% from baseline.

- d. Potential Pitfalls: Data integrity is an issue for self-reported measures in the usual care group. The level of usage with the AF CARE plan may be suboptimal or AF CARE may be ineffective in meeting study aims.

e. Sustainability: Sustainability will be determined by participant engagement and efficacy.

References

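### BP and BMI outcomes are patient-reported in an open wait-list design, and the plan names the self-report problem without a remedy; staff-recorded values should be the analysis values, at least at Initial and Month 3

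*Combined protocol and SAP*

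**What the plan says.** The schedule table in section c (Procedure) lists "Biometrics- pt reported (BP, HR, RR, waist, BMI") at Initial and Months 3, 6 and 12. Measurable Outcomes, item a, makes these values part of the cardiovascular risk factor (CVRF) outcome: Life's Simple 7 (LS7), "along with patient reported blood pressure, BMI, blood tests (lipids and glucose), and 6-minute walk test". CVRF is one of four efficacy domains and is secondary to feasibility (Research Design).

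On timing, section c states "Once consented, demographics, biometrics and baseline measures will be collected". Participants then enter their first responses in the app "and then will be randomized to either the digital platform AF CARE group" or the wait list. "The UC wait list group will receive usual care for the first 3 months", after which that group also gets the app.

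Section d (Potential Pitfalls) says "Data integrity is an issue for self-reported measures in the usual care group". The text then turns to app usage. No verification, order of preference between data sources or sensitivity analysis follows.

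The same schedule marks "Medical History and Physical" and "6 Minute Walk Test" at all four visits. The documents do not say that BP or weight recorded by staff at these visits is used for analysis.

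**The concern.** The documents describe no blinding or sham. For the first three months one arm receives messages twice a week and the other does not. The documents do not state that participants know their arm, but it is a safe inference. Someone who knows their arm may report BP or weight differently because of it.

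Initial values precede randomization, so knowledge of arm cannot affect them. Month 3 values can be affected, and Month 3 closes the only period in which one arm has the app and the other does not. The schedule has no blood tests at Month 3. Of the listed CVRF measures at that visit, this leaves only the walk test neither labelled patient-reported in the schedule nor built on LS7 questions.

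At stake is the validity of the BP and BMI effect sizes, which the Purpose and Research Design sections give as a reason for the randomized comparison.

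**Working it through.** The plan derives no figure on this point, so there is none to reproduce. The arithmetic below shows what an arm-related reporting error would do if one existed.

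**Inputs from the documents:** 60 patients (Research Design, Sample); a future trial with 80% power for a 10% change (Data Analysis). The allocation ratio, SD and alpha are not given.

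**Assumptions:** no true effect; two-sample t-test on change to Month 3; two-sided 5%; 30 per arm, with 24 per arm (20% loss, 30 × 0.8) and 20/40 as alternatives. The bias b is the between-arm difference in mean reporting error at Month 3, in SDs of the change score, set at 0.1, 0.2 or 0.3.

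**Formulas.**
- Expected observed difference = true difference + b. Sample size does not enter b.
- SE = √(1/n₁ + 1/n₂) in SD units. At 30/30: √(2/30) = 0.258; 95% half-width 0.517.
- False-positive rate: noncentral t with noncentrality b√(n₁n₂/(n₁+n₂)). At 30/30 this is b√15, or 0.39, 0.77 and 1.16.
- Bias share of mean squared error (MSE) = b²/(b² + SE²). At 30/30 and b = 0.2: 0.04/(0.04 + 0.0667) = 0.375.

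| Arms | SE | False-positive rate at b = 0.1 / 0.2 / 0.3 | Bias share of MSE |
|---|---|---|---|
| 30/30 | 0.258 | 6.7% / 11.9% / 20.8% | 13% / 38% / 57% |
| 24/24 | 0.289 | 6.3% / 10.4% / 17.4% | 11% / 32% / 52% |
| 20/40 | 0.274 | 6.5% / 11.1% / 19.0% | 12% / 35% / 55% |

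A simulation with 200,000 runs agrees with these false-positive rates to within 0.1 percentage point.

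**Carry-over to the next trial, if it is sized on the pilot effect.** The number per arm for 80% power is about 2(1.960 + 0.842)²/d² = 15.70/d², raised slightly for the t distribution. Assume a true effect of 0.4 SD.
- No bias, d = 0.4: 15.70/0.16 = 98.1, giving 100 per arm.
- b = +0.1, d = 0.5: 15.70/0.25 = 62.8, giving 64 per arm, with real power of about 61%.
- b = −0.1, d = 0.3: 15.70/0.09 = 174.4, giving 176 per arm.
- For comparison, one pilot standard error and no bias (d = 0.4 ± 0.258): 38 or 782 per arm.

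**The case against.** The strongest reply is that the harm is assumed. The documents contain no evidence of bias, and 0.1 to 0.3 SD is a chosen range that cannot be turned into mmHg or kg/m² without an SD. That stands: the figures are conditional.

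Second, a feasibility study seeks estimates, so false-positive rates are a poor yardstick, and the plan names matched-pair tests, not the two-sample test used here. This is fair. The MSE shares answer it better, and they show sampling error ahead of bias at 0.1 and 0.2 SD. Sampling error is also the larger threat to the next trial's size. But it shows in a confidence interval and shrinks with sample size; a reporting bias does neither.

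Third, if the next trial is sized on the fixed 10% change, a shift in the pilot's mean difference does not move that target. This also stands. The bias would still sit in the reported effect size.

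Fourth, the pitfall sentence does not mention knowledge of arm; it may mean completeness or accuracy without the app. Either reading leaves a stated weakness in one arm of a randomized comparison with no remedy.

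Finally, staff would not be blinded, some visits may be remote, and most of the self-report problem would remain. These limit the benefit of the fix but do not remove the reason for it.

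**Conclusion.** The concern holds. As written, the plan rests the Month 3 comparison of BP and BMI on values reported by participants who can tell their arm, and it acknowledges a self-report problem it does not address. The difference could be biased either way. Under the stated assumptions the effect runs from slight (6.7% false positives and 13% of MSE at 0.1 SD) to substantial (20.8% and 57% at 0.3 SD) at 30 per arm.

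The consequence is confined to part of one secondary domain. It does not touch the feasibility aim, and it reaches the multicenter trial only if that trial is sized on the pilot effect. The change is worth making because it is cheap. The absence of a remedy is clear from the text; the size of the harm is not known.

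**What to change.** In the schedule and in Measurable Outcomes a, state that staff measure and record BP and weight/BMI by one written procedure in both arms, at the visits that already include a physical and a walk test (at least Initial and Month 3), and that these are the analysis values. Further:

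- Keep patient-reported values to drive app messages and as a supportive analysis.
- Compute change within one method only, never from a patient-reported Initial value to a staff-measured Month 3 value. This is why staff recording is needed at Initial too.
- If a visit is remote, flag the value, report flagged counts by arm, and repeat the Month 3 comparison without them.
- Waist may be added, since it is in the schedule, though it is not a listed outcome.
- Use a recorder unaware of arm where possible.
- Refer to this rule in Potential Pitfalls, and say there what it does not cover.

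**Cost:** a small recording burden at scheduled visits and no new visit. Staff values will be missing where visits are remote. Anyone already enrolled may have only a patient-reported Initial value and so no same-method staff change score. LS7, the symptom, quality-of-life and AF knowledge questionnaires, and the Patient Health Questionnaire-9 remain participant-completed, and the change does not blind staff. The Month 3 column also carries the label CA, so the plan should say when that visit's measurements fall relative to any ablation.
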